3.4.1.1.2 Secondary Efficacy Variables

3.4.1.1.2.1 Metabolic Response Rate

One of the aims of this study is to see if, by using FDG PET-CT to assess metabolic response, the number of patients requiring 4 cycles can be reduced. There are currently no well validated metabolic response criteria for PET-CT in seminoma. Hence, we will use the criteria for the assessment of response developed for the evaluation of lymphoma (see Appendix 2 in the protocol).

3.4.1.2.2. Overall Survival

Overall survival is defined as the time from date of enrolment to the date of death due to any cause. All deaths will be included, whether they occur on study treatment or following treatment discontinuation. For patients who have not died, OS will be censored at the date of last contact. Methods for handling censoring and for analysis are the same as those described for PFS.

4 Sample Size

The primary objective is to gain a preliminary indication on whether carboplatin AUC-10 is worthwhile considering in a phase III study, using the PFS rate as a criterion. A'Hern's single-stage procedure is used to estimate the number of patients required [3].

The primary outcome is the percentage of patients progression-free at 2-years. Therefore, all patients must have at least 2-years follow-up (unless they have died or their disease has progressed). A Medical Research Council (MRC) study [1] showed that PFS rate at 3 years in standard chemotherapy, bleomycin, etoposide, cisplatin (BEP), is 81%. It is also known that PFS rate at 2-years and 3-years are the same [2]. Carboplatin AUC-10 should not therefore have a 2-year PFS rate of 75% or less, and it would only be worth considering in a phase III study if the true rate were 90% or more. This information is used in A'Hern's single stage design to yield a sample size of 45 patients, with 80% power and one-sided test of significance at the 5% level. Here the statistical assumption of this design is that there is 80% chance of concluding that carboplatin AUC-10 is effective if the true response rate is 90% or more, but only a 5% chance of concluding it is effective if the response rate is 75% or less. To allow for a 10% drop-out rate the intention is to recruit up to 50 patients.

5 General Considerations

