3.4 Study Variables

3.4.1 Primary and Secondary Variables

3.4.1.1 Primary Efficacy Variables

3.4.1.1.1 Progression-Free Survival (PFS)

PFS is defined as the time between the date of enrolment to first evidence of disease progression based on central review or death, whichever occurs first. For patients who have not died or experienced disease progression at the end of study, PFS will be censored on the last date the patient was known to be progression-free. Patients with no post-baseline tumour assessment will be censored at the date of enrolment plus 1 day. The PFS time will always be derived based on scan/assessment dates not visit dates.

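### SAP 3.4.1.2.2 gives two incompatible censoring rules for overall survival: date of last contact, then the PFS rules

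*SAP*

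**What the plan says.** SAP 3.4.1.2.2 (Overall Survival) sets out four things in order:

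- The endpoint: "Overall survival is defined as the time from date of enrolment to the date of death due to any cause".
- The events: "All deaths will be included, whether they occur on study treatment or following treatment discontinuation".
- A censoring rule specific to OS: "For patients who have not died, OS will be censored at the date of last contact".
- A cross-reference: "Methods for handling censoring and for analysis are the same as those described for PFS".

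The PFS rules it points to are in SAP 3.4.1.1.1:

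- The general rule for men without an event: "PFS will be censored on the last date the patient was known to be progression-free".
- A special case, for men never reassessed after baseline: their PFS time stops one day after they enrol.
- Which dates count: "The PFS time will always be derived based on scan/assessment dates not visit dates".

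SAP 7.3.3 says that the OS analysis methods are those of SAP 7.2.1. That section covers Kaplan-Meier estimation, confidence intervals and the success rule, and gives no censoring dates. The SAP endpoint table (section 2) states the OS endpoint as a median survival time. A 2-year OS rate comes in only through the reference to 7.2.1.

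**The concern.** For a living man, last contact and last tumour assessment can be many months apart. Protocol 5.5 has clinic visits for 2 years after treatment. Protocol 5.3.2 and note 7 of the Study Flowchart (5.4) schedule CT at 1 and 2 years for complete responders. For a man with a residual mass they name a CT 2 months after the end-of-treatment PET-CT. If he is not a complete responder and has no surgery, they name no later scan.

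If an analyst dated OS by the PFS rules, such a man would leave the risk set at his last assessment if he lived, but would count as an event at his date of death if he died. Censoring would then depend on outcome.

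OS matters to the argument for the regimen. Protocol 1.1 and 1.2 and SAP 1.1 rest the case for single-agent carboplatin partly on overall survival being unchanged because relapses can be salvaged. The censoring date for that endpoint should not depend on which of two adjacent sentences the analyst follows.

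**Working it through.** **1. The plan's own figure.** The documents give no OS rate, OS event count or OS power. The only design figure is for 2-year PFS: 45 patients, success at 39 or more, 75% against 90%, one-sided 5%, 80% power (Protocol 11.2.1 and 11.5; SAP 4 and 7.2.1). Exact binomial:

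- P(X ≥ 39 | n = 45, p = 0.75) = 0.0446
- P(X ≥ 39 | n = 45, p = 0.90) = 0.8415
- 45 / (1 − 0.10) = 50

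The figure reproduces, 45 is the smallest n that meets both limits, and none of it depends on how OS is censored.

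**2. The two OS instructions side by side.**

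| Living patient | OS-specific sentence | PFS rules, if carried over |
|---|---|---|
| No progression, seen after last assessment | last contact | last assessment at which he was progression-free |
| No post-baseline tumour assessment | last contact | enrolment plus 1 day |
| Alive after progression | last contact | no date given |

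The third row is empty because the PFS censoring sentence is limited in scope: "For patients who have not died or experienced disease progression at the end of study, PFS will be censored on the last date" that he was known to be progression-free. Progression is a PFS event, so a relapsed man never reaches that rule.

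**3. How far apart the dates can be.** Take a man with an unresected residual mass who is not a complete responder, counting from the start of treatment. The last scheduled scan falls after 3 or 4 three-week cycles (63 or 84 days), up to 28 days to the PET-CT, and 2 months (about 61 days) to the CT. That makes 152 to 173 days, or about 5 to 6 months. Visits run to 24 months after treatment. With 4 cycles (about 2.8 months) that is about month 27.

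**4. Effect on 2-year OS (constructed example).** Assumptions, none given in the documents: 45 men, all d deaths at month 18, m survivors last assessed at month 6, everyone else followed to month 27. With all deaths at one time, the Kaplan-Meier estimate at 24 months is S = 1 − d / n, where n is the number at risk at month 18. Under last contact n = 45; under the PFS dates n = 45 − m.

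| d | m | Last contact | PFS dates |
|---|---|---|---|
| 2 | 10 | 43/45 = 95.6% | 33/35 = 94.3% |
| 2 | 15 | 43/45 = 95.6% | 28/30 = 93.3% |
| 2 | 20 | 43/45 = 95.6% | 23/25 = 92.0% |
| 3 | 10 | 42/45 = 93.3% | 32/35 = 91.4% |
| 3 | 20 | 42/45 = 93.3% | 22/25 = 88.0% |

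With 2 deaths, the number at risk at 24 months falls from 43 to between 33 and 23.

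**5. The relapse route.** This needs a rule that the SAP does not state: survivors censored at progression, with deaths still counted. Assume progression at month 9 and deaths at month 18.

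- 2 progressors, 1 of whom dies: 44/45 = 97.78% becomes 43/44 = 97.73%, a loss of 0.05 point. Two of 45 (4.4%) is close to the 2 of 40 (5%) in Protocol 1.3 and SAP 1.1.
- 5 progressors, 2 of whom die, plus 5 survivors with no post-baseline assessment: at risk 45 − 3 − 5 = 37, so 35/37 = 94.6% against 95.6%.
- 11 progressors, 3 of whom die, plus 5 such survivors: at risk 45 − 8 − 5 = 32, so 29/32 = 90.6% against 93.3%.

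Across the constructed sets (2 to 11 progressors, 0 to 5 unassessed survivors, 1 to 3 deaths), the loss is 0 to 2.7 points.

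**6. Other readings of the cross-reference.** If the PFS rule is applied only to the men it covers and relapsed survivors stay in to last contact, relapse causes no bias. Five unassessed survivors then cost at most 0.8 point (37/40 = 92.5% against 93.3%). If everyone is cut at progression, later deaths are lost and OS is 100%, which is 2.2 to 6.7 points too high. That last reading contradicts the SAP's statement that all deaths are included.

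**The case against.** The strongest reply is that the SAP already states the right rule. The last-contact sentence is specific to OS, the next is general, and SAP 7.3.3 repeats the cross-reference for analysis methods only. An ordinary reader would take last contact plus Kaplan-Meier. This stands as far as it goes: no bias follows unless the general sentence overrides the specific one. It does not remove the conflict, because the cross-reference names censoring separately from analysis. As 7.3.3 already carries over the analysis methods, censoring is what the sentence in 3.4.1.2.2 adds.

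A reader might infer three stronger things that the documents do not support:

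- **That OS will be biased downward.** This is conditional on which sentence is followed, and step 6 shows readings with no bias from relapse and one with upward bias.
- **That salvaged men are the ones removed.** The PFS censoring sentence excludes men who have progressed. A date at or before relapse would be the analyst's invention.
- **That men with residual masses would be censored at month 6.** The PFS text speaks of scans or assessments and does not define assessment. Physical examination and tumour markers are scheduled at follow-up visits (Protocol 5.4 and 5.5), and the response definitions in Protocol Appendix 3 use markers. If these count, follow-up extends well past the last scan.

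Two limits on size also stand. The enrolment-plus-1-day rule should seldom apply, because the full analysis set requires follow-up data (SAP 5.2.1.1) and a day 17-21 PET-CT is planned for all. The named endpoint is median OS, and with survival at 88% to 96% the median is not reached under either rule.

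**Conclusion.** Wrong as written: an internal contradiction on a secondary endpoint. Two consecutive sentences set different OS censoring dates for living men seen after their last tumour assessment. The borrowed rule is unsuitable for OS and is undefined after progression.

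The consequence is conditional and probably small. In the step 4 examples the 2-year OS rate would fall by 1.3 to 3.6 points with 2 deaths (95.6% to between 94.3% and 92.0%), and by up to 5.3 points with 3 deaths (93.3% to 88.0%). Those figures rest on an assumed 10 to 20 of 45 men (22% to 44%) last assessed at month 6, a share that the documents do not give, and on deaths placed at month 18. Near the 5% relapse rate in the documents, the relapse route is worth about 0.1 point or less. Neither the 39-of-45 decision nor, in these examples, the median OS changes.

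**What to change.** In SAP 3.4.1.2.2, delete the words *handling censoring and for* from the cross-reference, so that only the Kaplan-Meier analysis method is shared with PFS. Then state that:

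- OS is censored solely at the date last known alive, from any contact, including contact after progression or further therapy;
- the PFS scan-date rule and the enrolment-plus-1-day rule do not apply to OS.

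This keeps the SAP's own last-contact rule. It costs a sentence or two of wording. Follow-up survival dates are already among the items source-verified for all patients (Protocol 10.2), so no new data are needed, and no sample size or decision rule changes. It is best done before any analysis for conference presentation (SAP 5.1 and 5.4), when follow-up is incomplete and even complete responders may be some months past their last CT.

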5.1 Timing of Analyses

The data will be analysed at the end of the study. No formal interim analyses are planned as the carboplatin AUC-10 is considered to be relatively safer than the standard chemotherapy. However, analysis may be performed for conference presentations after all patients have been recruited and treated, but have not completed the follow-up time. This may only be done after recruitment of all patients and completion of treatment and hence unlikely to affect the study.

5.2 Analysis Sets

5.2.1 Definition of Analysis Sets

Two analysis sets will be defined:

5.2.1.1 Full Analysis Set (FAS) population

The FAS will consist of all patients who completed at least one cycle of carboplatin AUC-10 and for whom relevant data is available at baseline and follow up. All efficacy analyses will be performed on the FAS population.

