## **3.0 Investigational plan**

### **3.1 Overall design**

This is a single arm phase II study to assess the safety, efficacy and toxicity of carboplatin AUC-10 in metastatic seminoma. Patients will be recruited from two sites.

Prior to the commencement of treatment, the patient should have a baseline PET-CT scan and a contrast enhanced CT scan performed within 28 days of study entry. Patients will be treated with carboplatin AUC-10 every 3 weeks (3 weeks=1 cycle) and on day 17-21 of the first cycle a repeat PET-CT scan will be performed. All PET-CT scans will be reviewed centrally and these results will determine how many further treatment cycles the patients will undergo. If the patient has a complete metabolic response [refer to Appendix 3], a further 2 cycles of carboplatin will be given, leading to a total of 3, and if the patient has not had a complete metabolic response but is responding, a further 3 cycles of carboplatin will be given [Refer to section 5.3.3 and page 20 (the table) for the timelines for the scans. Please refer to appendix 8 for the imaging protocol].

If no response is seen, then the patient will be taken off study and will receive conventional therapy using a cisplatin-based combination.

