### **3.4 *Target accrual***

Up to 50 patients will be recruited into the study (assuming 5 patients may withdraw for reasons other than disease progression) over four years. 45 evaluable patients will be necessary to establish activity of Carboplatin AUC10 in this setting.

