##### **4.4.1 *Data collection and follow up for withdrawn subjects***

CRFs should be sent to the Centre for Experimental Cancer Medicine, Barts Cancer Institute within one month of patient completing each cycle.

Subjects who are withdrawn are still evaluable for toxicity and efficacy if they have received at least one cycle of treatment and any data collected whilst receiving treatment will be used in the final analysis. Patients who are withdrawn from the study will be followed up for 2 years after treatment. Similarly, this follow up data will be used in the

final analysis. Any patients who decide to withdraw their consent will have no further data collected unless they have given express permission to do so.

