## 11.2 Statistical considerations

### 11.2.1 Sample Size

The primary objective is to gain a preliminary indication on whether carboplatin AUC-10 is worthwhile considering in a phase III study, using the progression free survival (PFS) rate as a criterion. A'Hern's single-stage procedure is used to estimate the number of patients required [8].

The primary outcome is the percentage of patients progression-free at 2-years. Therefore, all patients must have at least 2-years follow-up (unless they have died or their disease has progressed). An MRC study [1] showed that PFS rate at 3 years in standard chemotherapy, BEP, is 81%. It is also known that PFS rate at 2-years and 3-years are the same [2]. Carboplatin AUC-10 should not therefore have a 2-year PFS rate of 75% or less, and it would only be worth considering in a phase III study if the true rate were 90% or more. This information is used in A'Hern's single stage design to yield a sample size of 45 patients, with 80% power and one-sided test of significance at the 5% level. Here the statistical assumption of this design is that there is 80% chance of concluding that Carboplatin AUC-10 is effective if the true response rate is 90% or more, but only a 5%

chance of concluding it is effective if the response rate is 75% or less. To allow for a 10% drop-out rate the intention is to recruit 50 patients.

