3.1 General Study Design and Plan

This is a single arm phase II study to assess the safety, efficacy and toxicity of carboplatin AUC-10 in metastatic seminoma. Up to 50 patients will be recruited into the study over four years (assuming 5 patients may drop out for reasons other than disease progression/intolerable side effects). 45 evaluable patients will be necessary to establish activity of carboplatin AUC10 in this setting. Patients will be recruited for 48 months. Patients will be followed up as part of the study for 2 years following completion of treatment. The end of the study will be 3 months after the date when the last patient has completed his final follow up visit.

Prior to the commencement of treatment, the patient should have a baseline PET-CT scan and a contrast enhanced CT scan performed within 28 days of study entry. Patients will be treated with carboplatin AUC-10 every 3 weeks (3 weeks=1 cycle) and on day 17-21 of the first cycle a repeat PET-CT scan will be performed. If the patient has a complete metabolic response (see Appendix 3 of the protocol), a further 2 cycles of carboplatin will be given, leading to a total of 3, and if the patient has not had a complete metabolic response but is responding, a further 3 cycles of carboplatin will be given.

If a patient is showing no response to treatment then the patient will be taken off study and will receive conventional therapy using a cisplatin-based combination.

Figure 1: Treatment Flowchart

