5.2.1.2 Safety Set (SS) population

The SS will consist of all patients who meet the eligibility criteria and received at least one dose (cycle) of carboplatin AUC-10. Patients who did not receive any doses of study treatment will be excluded from the safety population. All safety analysis will be performed on the SS population.

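### The SAP Safety Set leaves out dosed but ineligible patients, and the literal FAS wording can leave an early death out of the 39/45 test

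*SAP*

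**What the plan says.** **Efficacy set.** SAP 5.2.1.1 defines the FAS as patients who "completed at least one cycle of carboplatin AUC-10 and for whom relevant data is available at baseline and follow up" and assigns all efficacy analyses to it. Protocol 11.3 sets the same two conditions. Neither says which data are relevant. Protocol 3.1 gives the cycle length: "Patients will be treated with carboplatin AUC-10 every 3 weeks (3 weeks=1 cycle". The pass rule in SAP 7.2.1 and protocol 11.5 is at least 39 progression-free among the first 45 patients at 2 years. Neither section says whether those 45 are counted by enrolment, by dosing or by FAS membership.

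Other sections bear on the same patients:
- SAP 3.4.1.1.1 runs PFS to "first evidence of disease progression based on central review or death, whichever occurs first". It also censors anyone without a post-baseline tumour assessment at enrolment plus 1 day, with no exception for deaths.
- Protocol 11.2.1: "all patients must have at least 2-years follow-up (unless they have died or their disease has progressed".
- Protocol 4.4.1: "Subjects who are withdrawn are still evaluable for toxicity and efficacy if they have received at least one cycle of treatment".
- Protocol 4.4 keeps withdrawn patients in the study for follow-up and analysis.

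**Safety Set.** SAP 5.2.1.2 takes "all patients who meet the eligibility criteria and received at least one dose (cycle) of carboplatin AUC-10". Protocol 11.3 asks only for one dose and has no eligibility condition. Protocol 11.6 and the synopsis ask for at least one cycle.

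**The concern.** Both FAS conditions depend on what happens after the first infusion. A patient who dies on day 10 has been treated and has had a PFS event, yet on the plain wording he has not completed a cycle and may have no follow-up data. If he is left out and a later patient takes his place among the 45, a failure has been exchanged for a patient who may be a success. The exchange can only favour the drug, and a single-arm trial has no control group in which the same exclusion would operate. The rule tolerates six failures (45 − 39), so a result near the boundary is sensitive to one patient.

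The Safety Set problem is a direct conflict between the two documents. A patient who was dosed and later found ineligible is in the protocol's set but not in the SAP's. Since the FAS carries no eligibility condition, the same man could count for efficacy while his adverse events are missing from the safety tables.

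**Working it through.** **Inputs.** From protocol 11.2.1 and SAP 4: unacceptable rate 75%, target rate 90%, one-sided 5%, power 80%, 45 patients, 50 recruited. From SAP 7.2.1: cut-off 39. The share of treated patients who fail before completing cycle 1 is not in the documents. It is an assumption here, taken from 0% to 2%.

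**1. The plan's own figure.** With X binomial:
- P(X ≥ 39 | 45, 0.75) = 0.0446
- P(X ≥ 39 | 45, 0.90) = 0.8415
- 45 / (1 − 0.10) = 50

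The smallest exact design meeting 5% and 80% is n = 45 with cut-off 39, so the stated design reproduces.

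**2. Early failures left out and replaced.** Let the true rate among all treated patients be 0.75 and let a share s fail early and be omitted. All omitted patients are failures, so the rate among those kept is 0.75 / (1 − s). With replacement up to 45, the false-positive rate is P(X ≥ 39 | 45, 0.75 / (1 − s)).
- s = 0: rate 0.7500, false-positive 0.0446
- s = 0.005: rate 0.7538, false-positive 0.0501
- s = 0.01: rate 0.7576, false-positive 0.0562
- s = 0.02: rate 0.7653, false-positive 0.0706

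In 50 treated patients these shares correspond to an expected 0, 0.25, 0.5 and 1 omitted patient (50 × s).

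**3. One patient at the boundary.** The exact one-sided 95% lower limit L solves P(X ≥ x | n, L) = 0.05.
- 39/45: L = 0.7537, above 0.75
- 39/46 (the omitted failure added back): L = 0.7331, below 0.75

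If the rule instead means the first 45 treated, adding him back displaces the last patient. If that patient was a success the count becomes 38/45 (L = 0.7276; P(X ≥ 38 | 45, 0.75) = 0.0941) and the trial is negative. If he was a failure the count stays at 39/45 and the verdict does not change. The probability of landing exactly on 39/45 is 2.7%, 8.7%, 16.4% and 13.4% at true rates of 75%, 80%, 85% and 90%.

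**4. Safety Set.** No arithmetic applies, because the documents give no rate of dosed but ineligible patients. The comparison is textual:
- protocol 11.3: dosed
- SAP 5.2.1.2: dosed and eligible
- FAS in both documents: no eligibility condition

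**The case against.** The case against the FAS half is substantial.
- Each cycle is a single day-case infusion, and SAP 5.2.1.2 treats dose and cycle as equivalent. On that usage one infusion satisfies the cycle condition, and only the undefined data condition could exclude anyone.
- The first scheduled response scan is on day 17-21, and footnote 3 of the protocol 5.4 flowchart allows it up to a week after day 21. Scheduled imaging can hardly document progression before cycle 1 ends, so the patients at risk are mainly those who die within three weeks of the first dose.
- Protocol 1.3 reports 2 relapses in 40 patients at this dose and mentions no early death.
- Protocol 4.4 keeps withdrawn patients, including those withdrawn for progression, in the analysis. Protocol 3.4 sets the recruitment allowance by "assuming 5 patients may withdraw for reasons other than disease progression", which implies that patients who progress stay among the 45.
- Survival and progression dates are source-verified for every patient (protocol 10.2), and a recorded death can fairly be read as follow-up data.

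These points stand as limits on size and likelihood. They do not settle the wording, because no section says that an early failure stays in the FAS.

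On safety, full verification of eligibility (protocol 10.2) and the deviation listing (SAP 5.2.2) should keep the number small. A deviation listing does not return a patient's adverse events to the tables.

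A reader might infer that the plan sets out to discard failures, or that any early stop is a lost failure. The documents support neither. Exclusion is one literal reading set against several passages pointing the other way, and stopping for toxicity without progression is not a PFS event.

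**Conclusion.** Both wording defects are real and should be fixed. The Safety Set conflict is plain on the page, and its effect cannot be quantified. The FAS wording permits, but does not require, the omission of a dosed patient who fails before completing cycle 1.

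The effect on the primary test is probably small. It is nil if there are no such patients, and the false-positive rate reaches 7.1% at an assumed 2% share. These figures assume a true all-treated rate of 75%, that every early failure is omitted, and that each is replaced up to 45. The error rate depends on that underlying share, so one omitted patient does not show that the test as a whole was badly inflated. What one omission can do is change the verdict when the result lies on the boundary. A reader might conclude that the 39/45 design is itself unsound. It is not: its figures reproduce, and the defect lies only in who is counted.

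**What to change.** - In SAP 5.2.1.2, delete the eligibility condition so that the Safety Set matches protocol 11.3.
- In SAP 5.2.1.1 and protocol 11.3, replace the completed-cycle and data-availability conditions with receipt of at least one dose. Align protocol 4.4.1, protocol 11.6 and the synopsis.
- State that death or documented progression at any time from enrolment to the 2-year point is a failure in the 39/45 count. Limit the enrolment-plus-1-day censoring in SAP 3.4.1.1.1 to patients alive without progression.
- Define the first 45 as the first 45 dosed patients in order of enrolment, and keep the cut-off of 39 (alpha 4.5%, power 84% when status is known for all 45).
- Report how many of those 45 have unknown 2-year status. Give the Kaplan-Meier estimate and a sensitivity count that treats them as failures. Do not choose the 45 by known status: a failure is known at once while a success needs two years of follow-up, so that would bring post-dosing selection back.

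The cost is a few phrases in each document and one sensitivity count, with no new data. Reported PFS and toxicity may look slightly less favourable.
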